9.3.3. Exposure

Exposure definitions will use the following variables:

- **VKA** will be defined as B01AA ATC code;
- **DOAC** will be defined as B01AF01 ATC code for rivaroxaban and B01AE07 ATC code for dabigatran;
- **DOAC high dosage** will be defined using CIP codes for rivaroxaban 20mg and dabigatran 150mg;
- **DOAC low dosage** will be defined using CIP codes for rivaroxaban 15mg and dabigatran 110mg;
- **Treatment group** will be defined by the first anticoagulant dispensation during the inclusion period, i.e. rivaroxaban high or low dosage, dabigatran high or low dosage, or VKA;
- **Index date** will be defined as the date of the first dispensation of the anticoagulant in the treatment group;
- **Duration of a drug dispensation** will be defined as the number of daily doses for DOAC and 30 days for VKA;
- **Drug (DOAC or VKA) exposure** will be defined as the period starting at the index date and ending at the date of the last drug dispensation plus the duration of the last drug dispensation for subject with a drug discontinuation (defined below) or at the date of drug switch (defined below), or at the end of follow-up, whichever is the earliest;
- **Drug (DOAC or VKA) discontinuation** will be defined with a grace period of 60 days for the main analysis and 30 days for a sensitive analysis after the last dispensation plus the duration of the last drug dispensation;
- **Drug (DOAC or VKA) switch** defined as a dispensation of another anticoagulant, including heparin and LMWH dispensation (B01AB ATC code), for subject with a drug discontinuation;
- **Post drug (DOAC or VKA) exposure** will be defined as the period starting at date of the end of drug exposure (see above) and ending at the date a new prescription of an anticoagulant or at the end of follow-up, whichever is the earliest;
- **DOAC compliance** will be estimated using Medication Possession Ratio (MPR) during drug exposure defined by the number of defined daily doses dispensed, divided by the number of days of drug exposure for DOAC. Considering the variable dosage of VKA between subjects and over time in individual subjects, no defined daily dose can be defined, and therefore no MPR for VKA exposure.
- During a hospitalisation, drugs are provided by the hospital, and this time will be taken into account for calculation of drug exposure and drug discontinuation.

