9.7.1. Generalities

The main analysis will be performed with the specific NVAF matched cohorts and a grace period of 30 days for the drug discontinuation definition. A secondary analysis will be performed using a statistical adjustment with all specific NVAF subjects, and a grace period of 30 days for the drug discontinuation definition.

The following sensitive analyses will be performed for matched cohorts, as well as all for statistical adjustment with all subjects:

- With a grace period of 60 days for drug discontinuation definition, in order to take into account the drug supply in real life, or short discontinuation and poor drug adherence;

- With the sensitive NVAF subjects and the two grace periods for drug discontinuation definition;
- With unspecified bleeding classified as haemorrhagic stroke for the specific and the sensitive NVAF cohorts.

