- **AF indication:** Anticoagulants are prescribed for several medical conditions. The main analysis will be done using the specific NVAF population, with a highly specific definition of the disease (LTD for AF or a hospitalisation with an AF diagnosis before the index date). Nevertheless, several subjects with an AF do not have an LTD and are not hospitalized or hospitalized for another primary diagnosis without AF reported in the linked or associated diagnosis, during the 3 years before index date. To assess the robustness of the main analysis results, secondary analyses will be performed using a sensitive definition for NVAF (sensitive NVAF population) defined as the subjects of the specific NVAF population, plus those with probable information using an AF disease score. In terms of bias, there is no reason that the specificity of AF definition will be different according to the treatment group.
- **Drug exposure:** VKA and DOAC exposure will be assessed using exhaustive non-hospital drug claims. Drugs prescribed during hospital stays are not recorded and could represent a potential risk of exposure underestimation. However, it should concern few subjects for a very short period of time, and the impact over a 3-year study period should be negligible. Drug expose is defined as the time between index date and the end of follow-up for subjects without drug withdrawal, i.e. as the time between index date and last dispensation + 90 days (30 days for the duration of the

last dispensation or less for small DOAC packaging, plus a grace period of 60 days), or before in case of drug switch. Two grace periods will be considered (60 and 30 days) to estimate the true drug withdrawal, in order to take into account the drug supply in real life, or short discontinuation and bad drug adherence that could be a risky situation for ischemic event, directly in relation with the use of the DOAC or VKA. This would also cover short hospital stays.

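### On-drug time ends at end of supply in 9.3.3 but at end of the grace period in 9.9, and the 9.3.3 rule classifies refill gaps by what happens later

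*Protocol*

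**What the plan says.** Section 9.3.3 starts drug exposure on the day of the first dispensation and describes it as "ending at the date of the last drug dispensation plus the duration of the last drug dispensation for subject with a drug discontinuation"; switch and end of follow-up are the other stopping points, if earlier. The abstract gives the same rule. The duration of a dispensation "will be defined as the number of daily doses for DOAC and 30 days for VKA". The grace period appears only in the definition of discontinuation, which "will be defined with a grace period of 60 days for the main analysis and 30 days for a sensitive analysis". Post-drug exposure is described as "starting at date of the end of drug exposure (see above) and ending at the date a new prescription of an anticoagulant"; it also stops when follow-up ends.

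Section 9.9, under Drug exposure, describes exposure "as the time between index date and last dispensation + 90 days". It breaks the 90 days down as 30 days for the "last dispensation or less for small DOAC packaging, plus a grace period of 60 days), or before in case of drug switch".

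The main comparisons in the Outcomes part of 9.7 are made during drug exposure, with Cox models for death and Fine and Gray models for clinical outcomes. Post-drug cumulative incidence is estimated separately.

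The length of the main grace period is itself inconsistent. Section 9.7.1 Generalities states: "The main analysis will be performed with the specific NVAF matched cohorts and a grace period of 30 days for the drug discontinuation definition". That is a separate matter, but it sets how many days are at stake here.

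**The concern.** There are two problems.

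**Two rules for time at risk.** Every primary on-drug comparison depends on when exposure ends, and the protocol gives two answers. Because post-drug follow-up starts where exposure ends, the choice also moves person-time and events between the two analyses.

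**The 9.3.3 rule uses future information.** On any day in a gap, whether that day is on-drug depends on whether the subject refills before the grace period runs out. Someone who dies cannot refill, and someone who bleeds may be taken off the drug. Classification of the time at risk can therefore depend on the outcome. Section 9.9 justifies the grace period by noting that short interruptions and poor adherence are a risky situation for ischaemic events and belong to use of the drug. Under 9.3.3, an event in such a lapse followed by permanent stopping leaves the on-drug analysis.

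**Working it through.** **1. Length of the tail.** Take a 30-day supply (fixed for VKA in 9.3.3, and the figure used in 9.9).

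- 9.9: 30 + 60 = 90 days after the last dispensation, which reproduces its stated figure.
- 9.3.3: 30 days.
- Difference: 90 − 30 = 60 days per discontinuer. With a 30-day grace period it is (30 + 30) − 30 = 30 days.

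**2. Looking forward.** Consider two subjects who both run out of supply on the same day. One refills within the grace period, so the whole gap is on-drug. The other does not, so the gap is post-drug from its first day. Nothing known during the gap separates them.

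**3. Death, reading A: a death inside the window means not discontinued.** Exposure then runs to death. Survivors of the window are cut back to end of supply, while those who die in it keep their deaths on drug. With hazard h, grace g and discontinuation rate d, the on-drug rate is about h × (1 + d × g). Inputs: h = 3.5 per 100 person-years (9.5, earlier VKA study); d is assumed, since the protocol gives no value.

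| d per person-year | g = 60 days | g = 30 days |
|---|---|---|
| 0.3 | 3.5 × (1 + 0.3 × 60/365.25) = 3.67 | 3.59 |
| 0.6 | 3.84 | 3.67 |
| 0.9 | 4.02 | 3.76 |

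If the true hazard ratio is 1 and one arm has d = 0.3 while the other has 0.6 or 0.9, the apparent ratio at 60 days is 1.049/1.099 = 0.96 or 1.049/1.148 = 0.91. At 30 days it is 1.025/1.049 = 0.98 or 1.025/1.074 = 0.95. Under this reading the start of post-drug time contains no deaths. One-year post-drug death risk is then multiplied by about (365.25 − 60)/365.25 = 0.836, or 0.918 at 30 days: an understatement of about 16% or 8%.

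**4. Death, both readings, by simulation.** Setup: no true difference on and off drug; 150,000 subjects; 730 days; 30-day supplies. Assumed: permanent stop after 2% to 8% of dispensations, late refill after 20% to 50%, gap length uniform up to the grace period. Reading B assigns a death inside the window to discontinuation at end of supply, while refilled gaps are still bridged. True rate 3.5 per 100 person-years.

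| Rule | Grace | On-drug | Post-drug |
|---|---|---|---|
| 9.3.3, reading A | 60 days | 3.6–4.0 | 2.9–3.1 |
| 9.3.3, reading B | 60 days | 2.4–3.0 | 4.1–10.4 |
| 9.3.3, reading A | 30 days | 3.6–3.7 | 3.2–3.3 |
| 9.3.3, reading B | 30 days | 2.8–3.2 | 3.7–7.0 |
| 9.9 | 30 or 60 days | 3.4–3.6 | not computed |

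Reading B is biased because survived gaps contribute on-drug person-time while deaths in gaps are excluded. Without late refills that mechanism disappears and reading B returns about 3.5.

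**5. Non-fatal bleeding.** Same approach, with clinically relevant bleeding at 2.6 per 100 person-years (9.5), 60 days' grace, 4% stopping and 50% late refills.

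| Share of gap bleeds that stop treatment | On-drug (9.3.3) | Post-drug (9.3.3) | On-drug (9.9) |
|---|---|---|---|
| 0% | 2.6 | 2.6 | 2.6 |
| 50% | 2.2 | 3.8–3.9 | 2.6 |
| 100% | 1.8 | 4.7–4.8 | 2.6 |

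**6. Scale.** The table in 9.5 gives detectable hazard ratios of 0.87 and 1.13 at 4% incidence with 20,000 per group. On the log scale, 0.91 is ln(0.91)/ln(0.87) = 0.68 of the lower limit. The 30-day values of 0.98 to 0.95 are smaller.

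**The case against.** The 9.9 sentence is garbled: it opens by speaking of subjects without withdrawal, and it sits in the limitations section, while 9.3.3 and the abstract agree with each other. A drafting slip in 9.9 is plausible. It nevertheless states what exposure is, and includes the grace days in it, so it cannot be read as merely the threshold for declaring discontinuation. Treating it as a slip would also leave the forward-looking rule in place.

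Section 9.6 leaves decision rules and exposure detail to the SAP. How a death inside the window is classed may properly be settled there, and its absence is not held against the protocol. But an SAP cannot follow two incompatible end dates that the protocol has already fixed.

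A reader might infer that 9.3.3 necessarily inflates on-drug mortality and makes the first 30 or 60 post-drug days death-free. The document does not support that: both follow only from reading A, and reading B reverses the direction when late refills occur. Nor are gap bleeds lost. They move to the post-drug period, which the objectives and 9.7 analyse and report. Non-fatal outcomes are unbiased if the event does not change refilling, and the protocol gives no figure for how often it does.

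The spurious hazard ratios need a two- to three-fold difference in stopping between arms, which is assumed. The fixed 30-day VKA supply against counted DOAC doses makes unequal apparent gaps possible for rivaroxaban versus VKA, but that asymmetry does not apply to rivaroxaban versus dabigatran.

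**Conclusion.** The contradiction is real and needs correcting before analysis: 60 days per discontinuer (30 with the shorter grace period) are on-drug under 9.9 and post-drug under 9.3.3. The 9.3.3 rule is also unsound in its own right, because later refilling decides whether gap time counts.

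The direction of the bias in death rates is not determined by the protocol. Against a true 3.5 per 100 person-years with 60 days' grace, the on-drug rate is 3.6 to 4.0 under one classification and 2.4 to 3.0 under the other. Bleeding and stroke are affected only to the extent that an event in a gap leads to stopping. Between-arm hazard ratios are affected only if gaps or stopping differ by arm; 0.96 to 0.91 (60 days) and 0.98 to 0.95 (30 days) illustrate the first classification only. All these sizes rest on assumed stopping and refill rates and on a constant hazard on and off drug. Varying the grace period between 30 and 60 days, as planned, changes the window but does not remove the dependence on later refilling.

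**What to change.** State one prospective rule in the abstract, 9.3.3 and 9.9. Exposure ends at last dispensation plus supply plus grace period for every subject, or at switch, death or end of follow-up if earlier. All events and person-time up to that date count, whatever happens afterwards, and post-drug follow-up starts on that date. This needs only past dispensing to decide whether a given day is on-drug, and it settles how a death or event inside the window is classed.

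As a sensitivity analysis, end exposure at the first end of supply without a refill for every subject, including those who refill later, with no gaps bridged. Bridging refilled gaps while cutting everyone else at end of supply would bring reading B back.

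The cost is protocol wording and programming. The drawback is that the main analysis attributes some off-drug days to the drug, which dilutes differences; the sensitivity analysis shows by how much.

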 - Investigation within 2 months before index date: Holter ECG monitoring or echocardiography, T3-T4 thyroid hormone test, D-dimer test or venous echo-doppler,
 - ≥ 1 drug dispensation within 3 months before index date for acetylsalicylic acid (ASA), ASA in association, clopidogrel, heparin or low-molecular-weight heparin (LMWH),
 - ≥ 1 drug dispensation within 2 months before or 2 months after index date of sotalol, other beta-blockers excluding associations, beta-blockers in association, verapamil or diltiazem, digoxin or digitoxin, other antiarrhythmic drug, other calcium channel blocker, agents acting on the renin-angiotensin system, diuretic.

Disease definitions for exclusion criteria

- Rheumatic valve disease (subjects excluded): Hospitalisation or LTD registration with rheumatic valve disease diagnosis, before index date (three-year history).
- Valve replacement (subjects excluded): Hospitalisation with diagnosis-related group of valve replacement or medical procedure for valve replacement (three-year history).
- Other probable indications of first anticoagulant dispensation (subjects excluded):
 - Treatment of VTE: index date within 2 months after hospital discharge

for pulmonary embolism or deep vein thrombosis;

- Prevention of VTE after orthopaedic surgery: index date within 2 months after hospital discharge for an orthopaedic surgery.

Exposure

- Treatment group: Defined by the first anticoagulant dispensation during the inclusion period, i.e. rivaroxaban high or low dosage, dabigatran high or low dosage, or VKA.
- Index date: Date of the first dispensation of anticoagulant in the treatment group.
- Duration of a drug dispensation will be defined as the number of daily doses for DOAC and 30 days for VKA;
- Drug exposure (rivaroxaban, dabigatran, or VKA): Period starting at the index date and ending at the date of the last drug dispensation plus the duration of the last drug dispensation for subject with a drug discontinuation or at the date of another anticoagulant dispensation (switch) or at the end of follow-up, whichever is the earliest.
- Drug (DOAC or VKA) discontinuation: with a grace period of 60 days for the main analysis and 30 days for a sensitive analysis after a “last” dispensation plus the duration of the last drug dispensation.
- Drug (DOAC or VKA) switch: Dispensation of another anticoagulant, including heparin and LMWH dispensation for subject with a drug discontinuation.

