- Post drug (DOAC or VKA) exposure: Period starting at date of the end of drug exposure and ending at the date a new prescription of an anticoagulant or at the end of follow-up, whichever is the earliest.
- DOAC compliance: Estimated using Medication Possession Ratio (MPR) during drug exposure defined by the number of defined daily doses dispensed, divided by the number of days of drug exposure for DOAC.
- During a hospitalisation, drugs are provided by the hospital, and this time will be taken into account for calculation of drug exposure and drug discontinuation.

Outcomes

- Stroke and SE: Hospitalisation with one of the two following primary diagnoses:
 - Ischemic or undefined stroke,
 - Other systemic arterial embolism or surgical procedure for systemic arterial embolism.
- Major bleeding: Hospitalisation with one of the three following primary diagnoses:
 - Haemorrhagic stroke,
 - Other critical organ or site bleeding (intraspinal, intraocular, retroperitoneal, intraarticular or pericardial, or intramuscular),
 - Other bleeding with a transfusion during hospital stay, or resulting in death.
- Clinically relevant bleeding (CRB): Hospitalisation with one of the five following primary diagnoses:
 - Haemorrhagic stroke,
 - Other critical organ or site bleeding (intraspinal, intraocular, retroperitoneal, intraarticular or pericardial, or intramuscular),
 - Gastro-intestinal bleeding,
 - Urogenital bleeding,

- Other bleeding.
- Death: All-cause death.
- ACS: Hospitalisation with one of the two following primary diagnoses:
 - Myocardial infarction (MI),
 - Unstable angina.

Potential confounding

- Gender and age at index date,
- CHA2DS2-VASc score (stroke risk factor score) at index date: Sum of points from congestive heart failure (+1), hypertension (+1), age \geq 75 years (+2), diabetes mellitus (+1), stroke or transient ischemic attack history (+2), vascular disease history (+1), age 65-74 years (+1), female gender (+1),
- CHADS2 score (stroke risk factor score for descriptive analysis) at index date: Sum of points from congestive heart failure (+1), hypertension (+1), age \geq 75 years (+1), diabetes mellitus (+1), stroke or transient ischemic attack history (+2),
- HAS-BLED score (bleeding risk factor score) at index date: Sum of points from hypertension (+1), abnormal renal function (+1), abnormal liver function (+1), stroke history (+1), bleeding history (+1), age > 65 years (+1), drug predisposing to bleeding (+1),

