9. RESEARCH METHODS

9.1. STUDY DESIGN

The design is a cohort study in a healthcare claims and hospitalisation database including new users of rivaroxaban, dabigatran, or VKA for SPAF with a follow-up for at least one year and up to two years per subject. The overall design of the study is presented in the following figure (Figure 1).

Data will be extracted from 1 January 2010 to 31 December 2015. The index date will be the first reimbursed dispensation of rivaroxaban, dabigatran, or VKA in 2013 or 2014, without dispensation of any of them within the 3 years before index date. The study follow-up period will start on the study index date and will end two years later, or until the date of death with a right censoring on 31 December 2015 (at least a one year follow-up period except for death). Rivaroxaban, dabigatran, and VKA exposure will be defined during the study follow-up period, as well as the occurrence of each of the study outcome.

The main advantages of this study are that data are collected independently of the research question, allowing the conduct of a nationwide population-based historical cohort. Limits of database analyses are discussed later (Section 9.9 Limitations of the research methods).

[figure not shown]

Figure 1: Study design

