9.7.6. Drug exposure

Description of drug use patterns including drug MPR for DOAC, dosage, treatment discontinuation, switch to another anticoagulant, co-dispensation of drug predisposing to bleeding, and one-year and two-year treatment maintenance for all and matched subjects according to the treatment group, with standardised difference for each comparison planned (rivaroxaban versus VKA, and rivaroxaban versus dabigatran).

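### The DOAC medication possession ratio counts the whole last box but divides by exposure cut at switch or death, so fully adherent patients cut early score well above 1

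*Protocol*

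**What the plan says.** Section 9.3.3 fixes both terms of the ratio. The numerator and denominator are "the number of defined daily doses dispensed, divided by the number of days of drug exposure for DOAC"; the abstract gives the same formula. Neither place states a cap or a rule for removing unused supply.

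The supply attached to a dispensation "will be defined as the number of daily doses for DOAC and 30 days for VKA". Exposure starts at the index date and finishes in one of these ways:

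- at discontinuation, "ending at the date of the last drug dispensation plus the duration of the last drug dispensation for subject with a drug discontinuation";
- otherwise "or at the date of drug switch (defined below), or at the end of follow-up, whichever is the earliest". The abstract words the switch limb as "at the date of another anticoagulant dispensation (switch) or at the end of follow-up, whichever is the earliest".

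Death enters through follow-up, which under section 9.1 "will end two years later, or until the date of death with a right censoring on 31 December 2015", with at least one year of follow-up for everyone who survives.

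The ratio is used in section 9.7.6, which plans a "Description of drug use patterns including drug MPR for DOAC, dosage, treatment discontinuation, switch to another anticoagulant" by treatment group, with standardised differences for each planned comparison. It is the only compliance measure in the protocol, and section 7 lists treatment compliance among the data that the Transparency Committee requested.

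Section 9.9, under drug exposure, describes a different end of exposure: last dispensation plus 90 days, made up of 30 days of supply and a 60-day grace period.

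**The concern.** The two terms of the ratio do not cover the same days. When a switch or death falls partway through a box, the doses left over for days after the cut stay in the numerator, but those days are not in the denominator. The ratio then exceeds 1 for a patient who took every dose on time, and the earlier the cut, the larger the excess. A value of 3 cannot be read as compliance.

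The size of the error depends on how and when a patient leaves treatment. A drug with more early switches or deaths would show a higher mean ratio at equal adherence, and a few very large values would inflate the SD on which the standardised difference rests. The figure affected is the one that would answer the Transparency Committee's request on compliance.

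**Working it through.** The protocol gives no value, target or cap for the ratio, so there is no figure of its own to reproduce. The check applies the stated definitions.

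**Inputs**
- Ratio, supply per dispensation and end of exposure: section 9.3.3 and abstract.
- End of follow-up at death, two years or 31 December 2015: section 9.1.
- 30-day boxes: the supply length used in section 9.9, which notes that some DOAC packs are smaller.
- Assumed here: refills exactly on time, so true compliance is 1.00, and doses in the numerator are counted in the same unit that sets the supply.

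**Exposure cut on day T**

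Ratio = 30 × ceil(T/30) / T.

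| T (days) | Doses dispensed | Ratio |
|---|---|---|
| 10 | 30 | 3.00 |
| 20 | 30 | 1.50 |
| 31 | 60 | 1.94 |
| 45 | 60 | 1.33 |
| 65 | 90 | 1.38 |
| 91 | 120 | 1.32 |
| 181 | 210 | 1.16 |
| 365 | 390 | 1.07 |
| 730 | 750 | 1.03 |

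For cuts spread evenly over days 1–30 the mean is 4.0 and the median 1.94. Over days 31–60 the mean is 1.37, and over days 91–180 it is 1.12. Administrative end of follow-up cannot come before about one year, so it contributes at most about 1.08. With 10-day packs the excess is smaller: 10/5 = 2.00 at day 5 and 20/15 = 1.33 at day 15.

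**Group level**

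Simulation of 400 000 patients per scenario, all perfectly adherent. Assumptions, none of them from the protocol: discontinuation at 0.30 per year, rounded up to the end of supply, and administrative end spread evenly between one and two years.

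| Switch-or-death hazard per year | Mean | SD | Median | Share above 1.2 |
|---|---|---|---|---|
| 0.05 | 1.03 | 0.4 | 1.013 | 0.9% |
| 0.10 | 1.05 | 0.6 | 1.015 | 1.9% |
| 0.20 | 1.08 | 0.8 | 1.018 | 3.6% |
| 0.30 | 1.11 | 1.0 | 1.021 | 5.4% |

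Patients who leave by switch or death average about 1.3.

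**Effect on the planned comparison**

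Take two equally adherent drugs with hazards of 0.10 and 0.30. The raw difference in means is about 0.062 and the SDs are 0.62 and 1.01. The pooled SD is √((0.62² + 1.01²)/2) = 0.84, so the standardised difference is 0.062/0.84 = 0.07. For hazards of 0.10 and 0.20 it is 0.04.

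**With supply trimmed to the exposure window**

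The day-10 case becomes 10/10 = 1.00 and the day-65 case 65/65 = 1.00. In the simulation every patient scores 1.00.

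**The other exposure window**

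For a patient who collects one box and never returns, 9.3.3 gives 30/30 = 1.00, while the window in 9.9 gives 30/90 = 0.33.

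**The case against.** The strongest reply is that the ratio is descriptive. It enters no outcome model, propensity score or primary or secondary outcome comparison, and the simulated effect on the standardised difference is small. This stands, and it sets the weight of the point. The inflated SD in fact shrinks the standardised difference, so the between-drug contrast is less exposed than the mean and SD themselves.

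A second reply is that section 9.6 leaves decision rules and calculated variables to the statistical analysis plan, which could cap or trim the ratio. That is possible. But the protocol already states the formula and the window, and an analysis plan that follows them literally reproduces the error.

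Third, 9.3.3 attaches a qualifier about discontinuation to its definition of a switch, which might mean that switches do not cut exposure mid-box. The abstract's wording supports the cut, and death cuts exposure on either reading.

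A reader might also infer more than the documents support:

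- *That every early leaver scores far above 1.* Patients who leave by discontinuation do not exceed 1 with on-time refills.
- *That a one-box discontinuer scoring 1.00 is an error, or that a patient with a 60-day refill interval who stops after two boxes should score 0.50 rather than 60/90 = 0.67.* The ratio is defined during exposure, and section 9.7.6 reports discontinuation and treatment maintenance alongside it. How long the last box really lasted cannot be seen in claims. This is a choice of convention.
- *That the exact values hold however a daily dose is defined.* The protocol does not equate the defined daily doses of the numerator with the daily doses that set supply. If one high-dosage reference per drug were used (an assumption), a low-dosage one-box patient would score 15/20 = 0.75 or 110/150 = 0.73.

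**Conclusion.** The concern holds in a limited form and is minor. As written, the ratio gives impossible compliance values for patients whose exposure is cut by switch or death within roughly the first few boxes: 3.0 at day 10 and 1.38 at day 65, with 30-day boxes and on-time refills. This distorts the mean and SD of the protocol's only compliance measure. Under the assumed hazards of 0.05 to 0.30 per year, the mean is about 1.03 to 1.11 and the SD 0.4 to 1.0 where every patient is equally and fully adherent. The medians barely move (1.013 to 1.021).

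The documents do not support a claim that the rivaroxaban–dabigatran comparison of compliance would be seriously misleading. A threefold difference in hazard, which is assumed, moves the standardised difference by only about 0.07, and the protocol gives no switch rate for either drug. No benefit-risk result is affected.

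**What to change.** In section 9.3.3 and the abstract, add one sentence: where exposure ends by switch, death or end of follow-up, the numerator counts only the doses that cover days inside the exposure period.

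State which end of exposure the ratio uses, and reconcile 9.3.3 (last dispensation plus its supply) with 9.9 (last dispensation plus 90 days). State also that the daily dose in the numerator is the one that sets the duration of a dispensation, if that is meant.

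Optionally, report the proportion of patients with a single dispensation next to the ratio. Trimming leaves these patients at 1.00 when they discontinue, and the proportion lets readers see how many there are.

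The cost is a sentence or two of text and a small programming change. No extra data are needed, and no other analysis changes unless the reconciliation alters the exposure window used elsewhere.
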